This is a non-randomized, unblinded dose-titration study. After consenting to participate, in addition to usual pharmacologic pain management, participants will receive 1 week of VR daily for 10 minutes per session, then 1 week of VR twice a day for 10 minutes per session, then 1 week of VR use as desired by the participants.

VR sessions will be administered using the Facebook (Facebook Inc., Menlo Park, CA) Meta Quest 2 VR and Touch controllers. This equipment was selected because it is portable, has built in audio, and has clear graphics at a lower price than VR setups that require a computer to generate graphics. The headset has an optional eyeglass spacer to allow participants to wear corrective eyeglasses during the

VR session if appropriate. The hand controllers facilitate immersive, interactive VR experiences. Of note, we considered using smartphone-based VR technology for this study; however, although technology continues to evolve, smartphone-based VR technology has not yet evolved enough to provide an adequately immersive VR experience to assure accurate results. The VR software, Nature Treks VR application (https://naturetreksvr.com) that features ten non-violent, nature-based experiences in peaceful environments (e.g. forest, river, beach, etc.) that can be played in a seated or fixed position. A Facebook/Meta account is currently required to login to the Quest 2 device; to protect patient privacy and ensure access to the Nature Treks application, the research team will activate the device with a dummy Meta account that does not contain any patient-specific information or payment information prior to distribution to participants. Participants will be provided with information on resetting the device to factory settings at the end of the study period if they wish to remove the dummy account and access the device using a personal Meta account for future, personal use of the device. Participants will not be prevented from searching for or downloading other VR programs onto the device during the study period, but will not be able to purchase software while logged into the dummy account.

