Because of the nature of the compared interventions, subjects and researchers cannot be blinded to intervention. Our primary outcome measure will determine the impact of VR on self-reported pain score in the last week (numeric rating scale, collected weekly). Self-reported pain experience remains the standard for clinical pain research. Secondary outcomes will measure pain interference (PROMIS Pain Interference Short Form, collected weekly), as-needed opioid use for patients taking opioid analgesics at the time of enrollment (self-reported using medication administration form), satisfaction with VR intervention and overall pain management (collected weekly), and survey of preferences for VR thematic content (collected after Week 4).

Following consent, subjects will complete baseline outcome assessments including self-reported pain score in the last week, the PROMIS Pain Interference Short Form, as-needed opioid use in the last week if applicable, and satisfaction with overall pain management. Subjects will then be provided with a VR headset and paired Touch controllers to bring home for the duration of the study and instructions on the frequency of use for each week. A member of the research will educate the patient on the technology and assure comfort with use. The research study coordinator will contact patients by phone at the end of each week to confirm dates and duration of use as specified by the study protocol, collect self-reported pain score in the last week, the PROMIS Pain Interference Short Form, as-needed opioid use in the last week if applicable, and satisfaction with the VR intervention and overall pain management. Additionally, participants will be surveyed on preferences for VR thematic content at the end of Week 3.

Participants will be monitored for adverse effects and harm for the duration of the study. Although well tolerated in previous studies of patients with cancer and advanced heart failure, potential risks may include dizziness, nausea, eye strain, and loss of confidentiality if data security is breached. Participants are instructed to only utilize the VR device while in a seated or reclined position and to never use the device when standing or ambulating due to the risk of potentially serious injury from falling.

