Participants will be compensated for their time and participation in this research; participants may keep the VR headset assigned to them for the study, and will receive a \$50 gift card upon completing the final survey at the end of Week 3. Participants will not be responsible for replacing or repairing the VR device if it is lost or damaged during the study period; a replacement device will be provided by the research team. Participants who wish to return the device may do so at their next scheduled appointment for usual care at MedStar Washington Hospital Center, where a member of the research team will collect it. Participants will not be required to schedule an appointment or return to MWHC for the purpose of returning the device. Participants who wish to return the device and are

unable or unwilling to return to MWHC for any reason will be provided with a prepaid shipping label by mail to return the device to the research team.

Results of this study will be used to determine the effect size, variance and variability to estimate sample size for a larger study. For this pilot study, a sample size of 60 is sufficient to provide accurate estimates of the information needed to calculate sample size for a future study. In the unanticipated circumstance that we are not able to accrue 60 participants during the study period, we will still be able to perform the desired analysis and calculate sample size for a future study if accrual is as low as 30 participants.

Funding for this study has been obtained through the Palliative Care Research Collaborative investigator Development Pilot Award (https://palliativecareresearch.org). The grant award is \$67,031 to support execution of the study over a 1-year period, beginning July 1 of 2022 and ending June 30, 2023.

DATA COLLECTION

Subjects will record daily use of the VR headset and duration of use for each session on a paper calendar provided to them at the time of enrollment. Subject survey data will be collected and entered by the research study coordinator using an online survey system accessible only to the research team (Tonic Health). Subjects will be assigned a de-identified code for survey entry. All data will be password protected and de-identified prior to analysis. Results will be reported in aggregate.

DATA SAFETY MONITORING PLAN

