Descriptive analyses will be performed to summarize baseline characteristics, including initial pain measures from self-report pain rating scale and PROMIS Pain survey. Preferences for VR thematic content and satisfaction with VR intervention will also be summarized. Summary statistics include frequency (%) for categorical variables and mean, standard deviations, median and IQR (1st and 3rd quartile) for continuous variables. Paired t-test or Wilcoxon sign rank test will be used to compare each

time point (end of weeks 1, 2, and 3) to the baseline (beginning of week 1) regarding pain score and PROMIS survey outcomes. Linear mixed-effects model will be used to assess the trend of pain score over the study period controlling for pain medication usage and other covariates (e.g., age, sex).

Data Collection Plan:

Time of Data Collection	Method of Data Collection+	Data Elements Collected
Beginning of Week 1 (Time of Enrollment)	Patient Survey (all patients)	 Self-reported pain score PROMIS Pain Interference Short Form As-needed opioid use* Satisfaction with overall pain management
End of Week 1	Patient Survey (all patients)	 Self-reported pain score PROMIS Pain Interference Short Form As-needed opioid use* Satisfaction with VR intervention and overall pain management
End of Week 2	Patient Survey (all patients)	 Self-reported pain score PROMIS Pain Interference Short Form As-needed opioid use* Satisfaction with VR intervention and overall pain management
End of Week 3	Patient Survey (all patients)	 Self-reported pain score PROMIS Pain Interference Short Form As-needed opioid use* Satisfaction with VR intervention and overall pain management Preferences for VR thematic content

* Data collected for patients receiving as-needed opioid analgesics at the time study enrollment

+ Patient survey administered by Research Coordinator by phone, data entered into Tonic Health

DATA SHARING

Data collected over the course will include summary findings of N = 60 enrolled participants. Per MHRI policy and in full alignment with NIH policy, all data compiled from this and future projects related to data collected in this study will be available upon request by any academic or government researcher, with data shared via existing pathways built to ensure transparency but protect participants. As part of the NIH data sharing directive, de-identified data from this study will be transferred to the PCRC De-Identified Data Repositories.

RECORD RETENTION

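### Sixty participants do not yield an accurate effect size for sizing the next trial, and the plan states no precision; the variance is estimated reasonably well

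*Combined protocol and SAP*

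**What the plan says.** The sample-size paragraph near the end of STUDY DESIGN AND METHODS gives the intended use: "Results of this study will be used to determine the effect size, variance and variability to estimate sample size for a larger study". It then asserts that "a sample size of 60 is sufficient to provide accurate estimates of the information needed to calculate sample size for a future study". If recruitment falls short, it says the team could still run the desired analysis and "calculate sample size for a future study if accrual is as low as 30 participants". So the two numbers carry different claims: accuracy at 60, feasibility at 30.

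No effect size, SD, alpha, power, precision target or dropout rate accompanies either number. DATA SAFETY MONITORING PLAN lists reasons for dropout as a reporting item, so some loss is foreseen.

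The design is one arm: "This is a non-randomized, unblinded dose-titration study". The primary outcome is the 0-10 pain score for the past week. DATA ANALYSIS says "Paired t-test or Wilcoxon sign rank test will be used to compare each" of the three weekly follow-ups with baseline, and adds a linear mixed model for trend. It lists means, SDs and quartiles as summaries. It does not mention confidence intervals, the SD of change or the correlation between baseline and follow-up, and it does not say which week supplies the planning effect size.

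**The concern.** The sufficiency sentence is the whole justification for the sample size, and it is a statement about precision that can be checked. Two inputs are promised, effect size and variance, and a sample of given size does not estimate them equally well. Required sample size varies as SD squared and as one over the standardised effect squared, so a moderate error in a small effect becomes a very large error in the next trial's size.

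If the observed effect is taken as accurate and put into a power formula, the larger trial could be far too small to detect the true effect, or far larger than needed. A reader of the plan would have no warning of this. Both 60 and 30 also count people enrolled, whereas a paired comparison uses only those with a baseline and a follow-up score.

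**Working it through.** **Inputs from the documents.** n=60, fallback 30; single arm; paired baseline-to-follow-up comparison of the pain score. There is no stated calculation behind 60, so there is no figure of the plan's own to reproduce.

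**Assumptions, not in the documents.** The successor is two-arm, 1:1, with 80% power and two-sided 5% alpha, and the paired effect d (mean change divided by SD of change) is used directly as its standardised difference. Observed d is taken from 0.4 to 1.0. A 20% loss is used for illustration.

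**1. Mean change.** The 95% half-width in SD units is t(0.975, n-1)/sqrt(n).
- n=60: 2.001/7.746 = 0.26
- n=48 (60 less 20%): 2.012/6.928 = 0.29
- n=30: 2.045/5.477 = 0.37

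**2. Effect-size route, the one the plan names.** The 95% CI for d comes from the noncentral t with n-1 df and t = d x sqrt(n). N per arm = 2(1.96 + 0.8416)^2/d^2 = 15.70/d^2, applied to each limit and rounded up.

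| Observed d | N per arm at d | 95% CI, n=60 | N per arm, n=60 | Fold | 95% CI, n=30 | N per arm, n=30 | Fold |
|---|---|---|---|---|---|---|---|
| 0.4 | 99 | 0.135 to 0.662 | 36 to 857 | 24 | 0.025 to 0.769 | 27 to about 26,000 | 978 |
| 0.5 | 63 | 0.23 to 0.77 | 27 to 298 | 11 | 0.12 to 0.88 | 21 to 1,165 | 57 |
| 0.8 | 25 | 0.51 to 1.09 | 14 to 62 | 4.6 | 0.38 to 1.21 | 11 to 108 | 10 |
| 1.0 | 16 | 0.69 to 1.31 | 10 to 34 | 3.6 | 0.55 to 1.43 | 8 to 52 | 6.7 |

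Fold is (upper limit/lower limit)^2, from unrounded limits.

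Two checks on robustness:
- With 80% intervals at d=0.5 and n=60, the range is still 35 to 152 per arm, or 4.4-fold.
- In a simulation of 50,000 pilots at a true d of 0.5 (true need about 63 per arm), the central 95% of planned sizes was 25 to 270 at n=60. About half of the pilots gave a size below the true need.

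**3. Variance route.** The 95% multipliers for the SD are sqrt((n-1)/chi-square quantile).
- n=60: sqrt(59/82.12) = 0.85 and sqrt(59/39.66) = 1.22. Squared, 0.72 to 1.49, a 2.1-fold span in N at a fixed difference.
- n=30: sqrt(29/45.72) = 0.80 and sqrt(29/16.05) = 1.34. Squared, 0.63 to 1.81, a 2.9-fold span.
- n=48: 0.83 to 1.25.

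**4. Accrual against paired scores.** With 20% lost from 60, 48 remain. At d=0.5 the interval is 0.20 to 0.80, which gives 25 to 404 per arm, or 16-fold rather than 11-fold.

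**The case against.** Several points on the other side stand.

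- A reader might infer that the plan calls 30 participants enough for accurate inputs. It does not. The word is attached only to 60; at 30 the text says only that the analysis and the calculation can be carried out, which is true. The extreme n=30 ranges therefore show the absence of a caveat, not a false claim.
- A reader might infer that neither input is delivered. The SD figures contradict that: a pilot of 60 estimates the variance reasonably well.
- The plan sets no threshold for accuracy and shows no calculation, so this is not an arithmetic mistake in a stated figure. It is an unsupported assertion that proves implausible for one of its two inputs.
- The fold ranges depend on an assumed d, and the documents do not describe the successor's design. A paired successor would halve N but leave the fold range unchanged, so the result does not turn on that choice. A large effect narrows the range, but only to 3.6-fold at d=1.0.
- Sizing the next trial is a stated use of the results. The PURPOSE section and the three aims concern pain impact, utilisation and satisfaction, so it would be wrong to treat planning inputs as the study's sole purpose.
- A confidence interval for an SD can be worked out from the SD and n. That makes the added reporting cheap; it does not make the sufficiency sentence correct.

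**Conclusion.** The sufficiency statement is unsupported as written and, for the effect size, not true in any ordinary sense of accurate. At n=60 the implied size of the next trial spans 24-fold at d=0.4, 11-fold at d=0.5, 4.6-fold at d=0.8 and 3.6-fold at d=1.0, given 95% intervals and the assumed two-arm successor. The variance part of the claim is acceptable: about 2-fold in N at 60 and 3-fold at 30 for a fixed difference.

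The fallback of 30 makes a weaker claim, but it carries no warning about precision and counts people enrolled.

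All of this is sampling error and would remain if the pre-post change were unbiased. Separately, an uncontrolled pre-post change does not estimate a between-arm effect, which is a further reason not to plan from it.

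The point deserves correction but falls below must-fix. It changes no outcome, test or safety rule of this study, and harm arises only if a later protocol uses the observed effect uncritically.

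**What to change.** **Sample-size paragraph.** Replace the sufficiency sentence with the precision actually obtained, by number of participants with both baseline and follow-up scores:
- 60: 95% half-width for mean change 0.26 SD; SD limits x0.85 to x1.22
- 48 (60 enrolled, an assumed 20% lost): 0.29 SD; x0.83 to x1.25
- 30: 0.37 SD; x0.80 to x1.34

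Express the fallback as participants with paired scores, give an expected loss rate, and name the week that supplies the planning estimates.

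**Use of the results.** State that the next trial will be sized on an important difference fixed in advance and on an upper confidence limit for the pilot SD, not on the observed pre-post effect. The confidence level is the sponsor's choice. As an illustration, a one-sided 80% limit multiplies the SD by 1.09 at 60, 1.10 at 48 and 1.14 at 30.

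**DATA ANALYSIS.** Add one table with the SD at each time point, the SD of change and the baseline-to-week correlation, each with a 95% confidence interval. The correlation matters if the successor adjusts for baseline.

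**Cost.** Revised wording, one table and a less favourable stated figure. No additional participants or assessments.

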The investigators and study coordinator will communicate weekly and meet at least twice monthly to discuss and address potential problems, ensure timely communication with the IRB if needed, and monitor study accrual. Two forms of recruitment materials will be generated: 1) patient-facing advertisement and recruitment material that are eye-catching and written to an 8th-grade reading level. Content will describe the study purpose, key eligibility criteria, and contact information for the study coordinator. Materials will be posted in WCI clinic and community areas where patients and caregivers are likely to be circulating; i.e., cafeteria, lobby, waiting areas and clinic rooms; 2) provider-targeted correspondence summarizing key study objectives and clearly outlining eligibility criteria, period of enrollment, study coordinator contact information, and highlighting the ongoing nature of the study. These materials will be distributed to WCI faculty and hematology/oncology medical fellows. The study coordinator will contact potentially eligible participants through participant self-referral or referral by the oncology team. The coordinator will screen the electronic health record to confirm eligibility, then schedule a time to meet with the participant. INCLUSION/EXCLUSION CRITERIA: Subjects will be considered for enrollment in this study if able to provide consent, at least 18 years old, and report moderate-severe pain (at least 4 out of 10 where pain is rated on a Likert scale between zero and 10) in the previous 7 days as a result of either cancer or cancer treatment. Palliative care consultation and/or referral to palliative care is not required for eligibility or participation. Additionally, participation will not be limited by whether subjects are receiving specific cancer-directed therapies at the time of enrollment. Subjects will be excluded if they already use VR for personal use, have intractable nausea/vomiting, history of motion sickness, history of seizures or epilepsy, have cranial structure abnormalities that prevent use of VR headset, or are currently enrolled in a palliative care or pain management study. Subjects will also be excluded if they have limited vision or vision defects that are not corrected with prescription eyeglasses, or if participants are unable or do not wish to wear required corrective eyeglasses with the VR headset. Informed consent will be conducted before enrolling each patient.

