Given the low-risk nature of this study, the PI and Co-PI will jointly ensure that the trial is conducted according to the approved protocols and report the incidence of any adverse events to other study team members, the designated Independent Safety Monitor (ISM), the Institutional Review Board (IRB), and the Georgetown-Howard Universities Center for Clinical and Translational Science Volunteer Participant Advisory Board (VPAB). The ISM will be experienced in clinical trials and familiar with the study intervention, will be appointed by the PI, and will not be involved in the study design, planning, or execution, or affiliated with the study sponsor. The PI will be responsible for submitting reports to PCRC and NINR. At any time, the PCRC and/or NINR may inspect summaries presented to/reviewed by the ISM.

The PI and Co-PI will compose regular data safety monitoring reports for review by the study Independent Safety Monitor (ISM) and the Georgetown-Howard Universities Center for Clinical and Translational Science Participant Advisory Board (VPAB). Content of report and frequency of review summarized in the following table.

Data type	Frequency of review	Reviewer
Subject accrual (including compliance with protocol enrollment criteria)	Quarterly	PI, ISM, VPAB

Data type	Frequency of review	Reviewer
Status of all enrolled subjects, as of date of reporting	Quarterly	PI, ISM, VPAB
Adherence data regarding study visits and intervention	Quarterly	PI, ISM, VPAB
AEs and rates	Quarterly	PI, ISM, VPAB
SAEs	Per occurrence	PI, ISM, VPAB, NINR/PCRC

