Study progress and safety will be reviewed every other week by the PI/Co-PI (more frequently if needed). Progress reports, including patient recruitment, retention/attrition, and AEs, will be provided to the Independent Monitor following each scheduled review, held quarterly at minimum. We will audit one complete case (informed consent through final survey collection) per quarter to assure compliance with IRB documents and include in the quarterly report for review. This quarterly report will also include a list and summary of AEs. In addition, the quarterly report will address (1) whether AE rates are consistent with pre-study assumptions; (2) reason for dropouts from the study; (3) whether all participants met entry criteria; (4) whether continuation of the study is justified on the basis that additional data are needed to accomplish the stated aims of the study; and (5) conditions whereby the study might be terminated prematurely. The quarterly report will be sent to the Independent Monitor and forwarded to the IRB and, if indicated, to the PCRC and/or NINR designated Program Officer. The PCRC will receive notifications are made to the IRB proposal and/or participant consent, the PI will alert the designated Program Officer for PCRC and NINR within 7 days.

To minimize risk associated with the study, we will take measures noted above to promote safety and independent monitoring of protocol adherence, data integrity, and AE reporting. Through the consent process, we will provide education to participants about potential risks associated with participation, as well as contact information for any additional questions, concerns, or reporting of AEs. The PI and Co-PI will continually monitor evolving literature related to VR interventions and relevant safety and/or ethical issues applicable to this study

During the funding of this study, any action by one of the study investigators, the IRB, or the VPAB that results in a temporary or permanent suspension of the study will be reported to the designated PCRC Program Official and the designated NINR Program Official within 1 business day of suspension.

DATA ANALYSIS

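### The quarterly AE check has no stated reference rate, and dizziness, nausea and eye strain are recorded neither before VR nor as items in the weekly surveys

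*Combined protocol and SAP*

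**What the plan says.** The Data Safety Monitoring Plan lists five matters for each quarterly report. The first is "whether AE rates are consistent with pre-study assumptions". The review table in the same section also schedules AEs and their rates for quarterly review.

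Study Design and Methods names the expected harms: "potential risks may include dizziness, nausea, eye strain, and loss of confidentiality if data security is breached". The prior evidence is a single clause, "Although well tolerated in previous studies of patients with cancer and advanced heart failure", and the monitoring plan opens with "Given the low-risk nature of this study". None of these statements carries a rate, a range or a level that would prompt action.

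On what is collected before VR, the same section says: "subjects will complete baseline outcome assessments including self-reported pain score in the last week, the PROMIS Pain Interference Short Form". As-needed opioid use and satisfaction complete the list. On who may enter, the Inclusion/Exclusion Criteria say that "participation will not be limited by whether subjects are receiving specific cancer-directed therapies at the time of enrollment", while excluding those who "have intractable nausea/vomiting, history of motion sickness". Every participant receives VR, and there is no concurrent control group.

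**The concern.** To judge whether an AE rate matches an assumption, the assumption must be written down first. Failing that, a comparator must be collected. In a single-group study the natural comparator is each participant's own state in the week before VR, and the plan does not record it for the symptoms it expects VR to cause.

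This matters because those symptoms may already be present. People on cancer-directed therapy or opioids can enrol, and nausea short of intractable is not a bar. Without a baseline, a report of nausea in Week 1 could be a VR effect, a worsening, or simply what the patient had before. The monitor would receive a count with nothing numerical to set it against. Pre-VR symptom status also cannot be recovered reliably once sessions have begun, whereas a missing assumed rate is only a matter of wording.

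**Working it through.** The plan states no AE figure, so there is none to reproduce. The first step is to look for the three symptoms wherever data are collected.

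| Source | Content | Dizziness, nausea or eye strain? |
|---|---|---|
| Enrolment survey | Average pain, as-needed opioid use, satisfaction, PROMIS Pain Interference | No |
| Week 1 and 2 surveys | The same four topics | No |
| Week 3 survey | The same four topics, then ease of use, enjoyment, immersion and content preferences | No |
| Data Collection Plan table (Data Analysis) | The same elements at all four time points | No |
| Health-record data | Demographics, cancer type, time since diagnosis, analgesic use | No |
| Weekly phone script | Closes with an open invitation to raise anything | Only if volunteered |
| Eligibility screen | Yes/no exclusions for intractable nausea/vomiting and motion-sickness history | Most severe nausea only; not graded |

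The second step is to ask how much the missing background rate matters. Let b be the background risk of a symptom over follow-up and v the risk added by VR, acting independently. The total risk is t = 1 − (1 − b)(1 − v), so v = 1 − (1 − t)/(1 − b). Suppose, purely for illustration, that 18 of the planned 60 participants report nausea: t = 18/60 = 30%, exact 95% interval 18.8% to 43.2%. The values of b are assumptions; the documents give none. The illustration also supposes that every case is captured.

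| Assumed background b | Implied VR risk v | Chance of 18 or more of 60 from background alone |
|---|---|---|
| 0% | 1 − 0.70/1.00 = 30% | 0 |
| 10% | 1 − 0.70/0.90 = 22.2% | about 0.00002 |
| 20% | 1 − 0.70/0.80 = 12.5% | 0.043 |
| 30% | 1 − 0.70/0.70 = 0% | 0.55 |

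The same count is thus strong evidence of VR harm at one background rate and unremarkable at another.

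The third step concerns the opposite error. The surveys contain no symptom item, so a symptom reaches the record only if the participant volunteers it or the general monitoring catches it. Under-counting is at least as plausible as over-counting, and the net direction cannot be determined from the documents.

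Finally, precision. With no events among n participants, the two-sided 95% upper bound is 1 − 0.025^(1/n): 6.0% for n = 60, 11.6% for the minimum accrual of 30, and 21.8% for n = 15. The last is one quarter's intake if 60 enrol evenly over the one-year funding period (60/4 = 15), which is an assumption. Even a repaired check will be coarse within a single quarter.

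**The case against.** The strongest reply is that this is a small, low-risk pilot whose aims are pain, utilization and satisfaction, and that safety oversight does not rest on one sentence. The quarterly report lists AEs and goes to an independent monitor who is familiar with the intervention and not involved in running the study, and to an advisory board; it is also forwarded to the IRB. SAEs are reviewed as they occur. Sessions last 10 minutes in Weeks 1 and 2, and participants log daily use and duration, so a symptom can be set against VR exposure. The most severe nausea and motion-sickness history are screened out.

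Much of this stands, and it rules out four stronger readings that a reader might infer:

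- That VR harm cannot be separated from illness at all. Exposure logs and clinical judgement may settle single cases, although the plan gives no attribution rule and the calendar is not described as recording symptoms.
- That the check can neither raise nor clear a signal. It can be read qualitatively against the stated low risk and the named harms, and the monitor sees the events themselves.
- That a predictable, large number of background symptoms will be logged as AEs. That would require every participant to be asked every week, which the surveys do not do, and a background rate that the documents do not supply.
- That a biased tolerability estimate passes to the larger study. The sample-size paragraph carries forward effect size and variability; no aim or planned analysis estimates an AE rate.

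The consent form was not among the documents reviewed, so whether it quotes any rates is unknown. What the reply does not supply is a reference rate, or any record of the three symptoms before VR.

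**Conclusion.** The point holds in a limited form. The first item of the quarterly report has no quantitative reference in the documents provided, and the data that could serve as one are not collected before VR or systematically afterwards. Reported dizziness, nausea or eye strain cannot be reliably classed as new, worse or unchanged.

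No size can be fixed from the documents. Under the assumed backgrounds of 0% to 30%, one and the same count of 18 in 60 is compatible with a VR-induced risk anywhere from 30% to zero. That range rests on the independence formula and on complete capture of symptoms, which the present surveys would not achieve. The primary pain analysis is unaffected. The change is worth making because it is cheap and because baseline symptoms that go unrecorded cannot be filled in later.

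**What to change.** Add three items to the enrolment survey and, in identical words, to each of the three weekly surveys: presence and severity over the last 7 days of dizziness, nausea and eye strain. The items are needed at both ends; baseline items alone would have nothing to be compared with.

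Record every report, and flag those that are new or worse than the participant's own enrolment answer. Reword the first item of the quarterly report so that it gives, for each symptom and each VR week, the number flagged divided by the number with both an enrolment and a that-week answer. Show anyone enrolled before the change separately, as having no baseline. If the present wording is kept instead, an assumed rate for each symptom and its source should be written down before enrolment. That supplies a reference but does not replace the missing baseline.

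The cost is about one extra minute at enrolment and on each of three calls, roughly 4 × 1 = 4 minutes per participant, plus one reworded sentence. The limit is that a single pre-VR week does not fully isolate VR harm: cancer therapy may change between weeks, and the order of VR frequencies is fixed, so comparisons by week remain descriptive.
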